### 8.2 Data Review Committee

#### 8.2.1 Safety Run-In

Pembrolizumab has not previously been combined with BGB324 in patients (in any indication) and therefore, a safety run-in will include a total of 12 patients.

A Data Review Committee (DRC), consisting of Principal Investigators, the Sponsors' (BerGenBio and Merck) Medical Monitors, and invited experts as required, will review all patient safety data after 6 patients have been enrolled and had the potential to be followed for 6 weeks (2 cycles), and then again after a further 6 patients (total 12 patients) have had the potential for 6 weeks follow-up. At each of these safety reviews, the DRC will consider the rate of BGB324 dose reductions and the rate of permanent discontinuation from BGB324 and pembrolizumab.

Each patient will have had the potential to receive (as a minimum):

- 2 cycles of pembrolizumab
- BGB324 at 400 mg for 3 days, followed by 200 mg daily for ~6 weeks

At the 1st safety run-in (based on 6 patients) the DRC will evaluate the need for dose modification for individual patients, or BGB324 loading or daily dose modification. A rate of >66% (4 or more) of patients requiring treatment to be dose reduced (BGB324) or permanently discontinued (either BGB324 or pembrolizumab, or both) will be considered as a significant rate.

The 2nd safety run-in (based on the 12 patients) the DRC will again evaluate the need for dose modification for individual patients, or BGB324 loading or daily dose modification. A rate of >40% (5 or more) of patients requiring treatment to be dose reduced (BGB324) or permanently discontinued (either BGB324 or pembrolizumab, or both) will be considered as a significant rate.

During the safety run-in reviews, the DRC will have the option to recommend a lower dose of BGB324 (dose level -1) for new patients. Dose level -1 is defined as 200 mg BGB324 on Days 1, 2 and 3 followed by 100 mg from Day 4 onwards.

Additionally, a review of emerging safety data from the whole BGB324 program will be made 6-monthly.

### **8.2.2 End of Stage 1 – Efficacy Analysis**

Recruitment to the study will be halted once 28 evaluable patients have been entered, and whilst the Stage 1 analysis is conducted. Recruitment will recommence if the decision is made to continue to the maximum of 56 evaluable patients.

The DRC will meet to review the overall risk/benefit profile of the combination, together with the ORR when 28 patients have had the potential to be followed for 24 weeks – and therefore these patients have the potential to have data from at least 2 post-treatment tumor-imaging assessments. The DRC will document the ORR and if it favors the null hypothesis for futility, or the alternative hypothesis for demonstration of activity, and recommend if the study should proceed to evaluate up to a further 28 patients. This recommendation will take into account the statistically-driven endpoint, in the context of on-going safety data review of the combination approach, as well as the quality of the response e.g. available data on duration of response (DoR) and progression-free survival (PFS), where possible.

Appropriate representatives of the Sponsor and the coordinating personnel may also attend and minute DRC meetings. Recommendations of the DRC will be documented and sent to the sites. Further details on the composition of the DRC, as well as the process for data review, issue of recommendations and decision making, are described in a separate DRC charter for this study.

### **8.3 Statistical Analysis Plan**

Detailed statistical analysis information will be provided separately in the Statistical Analysis Plan (SAP). The SAP will detail all data handling rules e.g. full definition of patient populations for analysis, including the management of missing values and the handling of data for patients lost to follow-up or missing other important information. The SAP will also outline protocol deviation criteria. Any deviations to the planned analyses specified or populations defined within the SAP will be justified in writing and presented within the final clinical study report. It will also describe the rules for handling of missing data points for the primary, secondary and exploratory endpoints.

An interim analysis will be performed after 28 evaluable patients have had the potential to have at least 24 week follow-up (enabling each patient to have the potential for at least 2 ‘on treatment’ disease assessment scans). Recruitment will be halted during this period and until the interim analysis has been conducted.

The SAP will fully describe the efficacy analyses and descriptive summaries that will be undertaken for both the interim and final analyses. All efficacy endpoints (ORR, DoR, PFS, DCR and OS) will be summarized and described for both the interim and final analyses. See [Section 8.11](#) and [Section 8.12](#) for further details.

Summaries of ORR by PD-L1 and Axl expression will be provided for both the interim and final analyses.

The clinical database lock for the final analysis will occur after the final patient has had the potential to be followed for 24 weeks and after all data are reconciled (i.e. “cleaned”) for all patients who participate in the study. A single clinical study report (CSR) will be generated. The SAP will be finalized and signed before the database lock.

An addendum (or addenda) to the CSR will be generated to report SAEs from patients remaining on treatment at the time of the LPLV patients to closure of the study (defined as every patient completing their study combination treatment) ([Section 8.6](#)).

The main data analyses intended for this trial are briefly described in this section and in [Section 8.11](#) and [Section 8.12](#). The SAP will provide full details of all planned data analyses for the primary, secondary and exploratory objectives of the study.

#### 8.4 Population

The efficacy objectives will include all evaluable patients. An evaluable patient will have received at least one combination dose and who have measurable disease at entry according to the Investigator Site assessment.

For all safety objectives, the safety set consisting of all patients that have received at least one dose of BGB324 and/or pembrolizumab will be used.

For some objectives (PK and biomarker) a subgroup of patients of the safety set with respective baseline and post-baseline measurements will be used.

Patients who signed a consent form and were screened but did not receive any treatment will be listed if they reported an AE in the time after consent and before treatment allocation ([Section 7.1](#)). All AEs that occur after the consent form is signed but before treatment allocation must be reported if they cause the patient to be excluded from the trial, or are result of protocol-specific intervention, including but not limited to, washout or discontinuation of usual therapy, diet, placebo treatment or a procedure ([Section 7.1](#)).

#### 8.5 RECIST 1.1 and Disease Assessment

Efficacy endpoints in this study, including ORR, DoR, PFS will all be based on tumor imaging evaluation by RECIST 1.1.

RECIST assessments will be performed using contrast-enhanced CT/MRI assessments of chest, abdomen, and pelvis. Additionally, x-ray, bone scans and brain scans will be used as appropriate.

Additional anatomy should be imaged based on signs and symptoms of individual patients at baseline and follow-up. Baseline assessments should be performed no more than 28 days before start of study treatment (although bone scans and brain scans may be done within 6 weeks), and ideally should be performed as close as possible to the start of study treatment.

All radiological and non-radiological (eg, MRI) scans will be reviewed by the local site investigator; and if possible, stored electronically (de-identified with the patient's notes) at site.

A maximum of 5 target lesions must be selected at baseline. All target lesions are measurable. Target lesions should be selected on the basis of their size (longest diameter for non-nodal lesions or short axis for nodal lesions), but in addition should be those that lend themselves to reproducible repeated measurements.

All remaining lesions present at baseline are considered non-target, irrespective of whether they are measurable.

Disease assessments will be performed every 9 weeks  $\pm 7$  days for the first 46 weeks relative to the date of first treatment administration and then every 12 weeks  $\pm 7$  days thereafter until confirmed objective disease progression as defined by RECIST 1.1 (irrespective of the reason for stopping treatment or subsequent therapy).

Any other sites at which new disease is suspected should also be adequately imaged at follow/up.

If an unscheduled assessment was performed and the patient has not progressed, every attempt should be made to perform the subsequent assessments at their scheduled visits. This schedule is to be followed in order to minimize any unintentional bias caused by some patients being assessed at a different frequency than other patients.

**Table 20** provides the RECIST 1.1 evaluation and definitions of disease response (based on TLs).

**Table 20: RECIST 1.1 evaluation and definitions of disease response**

Complete Response (CR)	Disappearance of all TLs since baseline. Any pathological lymph nodes selected as TLs must have a reduction in short axis to <10 mm.
Partial Response (PR)	At least a 30% decrease in the sum of the diameters of TLs, taking as reference the baseline sum of diameters
Stable Disease (SD)	Neither sufficient shrinkage to qualify for PR nor sufficient increase to qualify for PD
Progression of disease (PD)	At least a 20% increase in the sum of diameters of TLs and an absolute increase of at least 5 mm, taking as reference the smallest sum on study (this includes the baseline sum if that is the smallest on study).
Not Evaluable (NE)	Only relevant if any of the TLs were not assessed or not evaluable or had a lesion intervention at this visit. Note: if the sum of diameters meets the progressive disease criteria, progressive disease overrides not evaluable as a TL response

All patients who are considered to have had a complete or partial response must have this response confirmed by a confirmatory scan at least 4 weeks later.

Details of any new lesions will also be recorded with the date of assessment. The presence of one or more new lesions is assessed as progression, however, in the absence of clinical deterioration, treatment can continue. The suspected disease progression should be confirmed after 28 days.

A lesion identified at a follow up assessment in an anatomical location that was not scanned at baseline is considered a new lesion and will indicate disease progression.

The finding of a new lesion should be unequivocal: i.e., not attributable to differences in scanning technique, change in imaging modality, or findings thought to represent something other than tumor.

If a new lesion is equivocal, for example because of its small size, the treatment and tumor assessments should be continued until the new lesion has been confirmed. If repeat scans confirm there is a new lesion, then the progression date should be declared using the date of the initial scan.

Disease progression requires confirmation. The confirmatory scan should occur preferably at the next scheduled visit and no earlier than 4 weeks after the initial assessment of progression of disease (PD) in the absence of clinical deterioration.

The overall visit response will be derived using the algorithm shown in [Table 21](#).

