### 5.3.10 Tumor imaging

Efficacy endpoints in this study, including ORR, DoR, PFS will all be based on tumor imaging evaluation by RECIST 1.1.

RECIST assessments will be performed at the times given in Schedule of Study Assessment Table 4 and Table 5 using contrast-enhanced CT (preferred method) or MRI assessments of chest, abdomen, and pelvis. X-ray scans can be used where appropriate. Bone scans and brain scans should be conducted in the 6 weeks prior to study entry. Subsequently, x-ray, bone scans and brain scans will be used as appropriate. Additional anatomy should be imaged based on signs and symptoms of individual patients at baseline and follow-up.

Baseline assessments should be performed no more than 28 days before start of study treatment (6 weeks for brain and bone scans), and ideally should be performed as close as possible to the start of study treatment. The Screening imaging assessments must confirm the patient has measurable disease per RECIST 1.1 (see [Section 3.1](#)).

For each patient, the same modality used at Screening must be used serially throughout the duration of study participation. All imaging procedures will be performed according to standard local imaging protocols to ensure consistency across study assessments.

All radiological and non-radiological (e.g. MRI) scans will be reviewed by the local site investigator; and if possible, stored electronically (de-identified with the patient's notes) at site.

A maximum of 5 target lesions (TLs) must be selected at baseline. All target lesions are measurable. Target lesions should be selected on the basis of their size (longest diameter for non-nodal lesions or short axis for nodal lesions), but in addition should be those that lend themselves to reproducible repeated measurements. All remaining lesions present at baseline are considered non-target, irrespective of whether they are measurable.

Disease assessments will be performed as per the schedule described in [Table 3](#), [Table 4](#) and [Table 5](#) – that is, every 9 weeks  $\pm 7$  days for the first 46 weeks relative to the date of first treatment administration and then every 12 weeks  $\pm 7$  days thereafter until confirmed objective disease progression as defined by RECIST 1.1 (irrespective of a delay to treatment, or the reason for stopping treatment or subsequent therapy).

Any other sites at which new disease is suspected should also be adequately imaged at a follow-up visit.

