## 8 DATA EVALUATION: CRITERIA FOR EVALUATION OF OBJECTIVES

### 8.1 Statistical Considerations, Interim Analysis and Sample Size

The study will employ a  $k$ -stage single arm design, an approach derived from basic statistical theory. If  $p$  denotes the true tumor response rate with drug, the null and alternative hypotheses to be assessed in this trial are:  $H_0 : RR=p_0$  vs  $H_1 : RR=p_1$  ( $p_0 < p_1$ ), with  $p_0=0.20$  and  $p_1=0.35$ . To test these hypotheses, this trial is a  $k$ -stage single arm design with  $k=2$ , being an extension of Simon's 2-stage design. In this design with  $k=2$ , there are two analyses: a single interim and a final analysis. At the interim, the response rate is evaluated in a fixed number ( $m$ ) of patients using a predefined decision rule to determine if the study should stop for futility (in the situation where the null is confirmed) or for efficacy (in the situation where the alternative hypothesis is confirmed). If neither hypothesis is confirmed, a further fixed number of patients ( $l$ ) are assessed for response and a final analysis is performed on all ( $m+l$ ) patients. In both interim and final analyses, the response rate will be presented together with the associated exact 90% confidence interval (CI).

With  $p_0=0.20$  and  $p_1=0.35$ , the interim will be conducted with  $m=28$  patients. If 5 or fewer responses are observed in these 28 patients, the trial will be terminated in favor of the null for futility; however, if 11 or more responses are observed, then the trial will be stopped in favor of the alternative for demonstration of activity. Otherwise a further 28 patients may be evaluated, for a total of 56 patients. If a total of 17 or more responses are seen in 56 patients, then the null will have been rejected in favor of the alternative; otherwise the null will not have been rejected.

Based on 500,000 trial simulations, this design provides an overall power of 80.6% to test the stated null and alternative hypothesis with a 1-sided Type I error rate of 0.048. Under the null hypothesis, the probability of correctly stopping for futility at the interim is 50.2% and, under the alternative hypothesis, the probability of correctly stopping for activity at the interim is 38.4%. Consequently, the expected sample size for the design is 42-44 subjects.

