### 8.5.1 Immune-related RECIST 1.1 and confirmation of progression

RECIST 1.1 will be adapted to account for the unique tumor response characteristics seen with treatment of pembrolizumab. Immunotherapeutic agents such as pembrolizumab may produce antitumor effects by potentiating endogenous cancer-specific immune responses. The response patterns seen with such an approach may extend beyond the typical time course of responses seen with cytotoxic agents, and can manifest a clinical response after an initial increase in tumor burden or even the appearance of new lesions. Standard RECIST may not provide an accurate response assessment of immunotherapeutic agents such as pembrolizumab. Therefore, RECIST 1.1 will be used with the following adaptations:

If radiologic (or non-radiological) imaging suggest that the patient has progressive disease (initial PD), tumor assessment should be repeated  $\geq 4$  weeks later in order to confirm PD with the option of continuing treatment per below while awaiting radiologic confirmation of progression.

- If repeat imaging shows  $<20\%$  tumor burden compared to nadir, stable or improved previous new lesion (if identified as cause for initial PD), and stable/improved non-target disease (if identified as cause for initial PD), treatment may be continued/resumed;
- If repeat imaging confirms PD due to any of the scenarios list below, patients will be discontinued from study therapy.

In determining whether or not the tumor burden has increased or decreased, site study team should consider all target lesions as well as non-target lesions.

Scenarios where PD is confirmed at repeat imaging:

- Tumor burden remains  $\geq 20\%$  and at least 5 mm absolute increase compared to nadir;
- Non-target disease resulting in initial PD is worse (qualitative);
- New lesion resulting in initial PD is worse (qualitative);
- Additional new lesion(s) since last evaluation.

In patients who have initial evidence of radiological PD, it is at the discretion of the treating physician whether to continue a patient on study treatment until repeat imaging is obtained. This clinical judgment decision should be based on the patient's overall clinical condition, including performance status, clinical symptoms, and laboratory data. Patients may receive pembrolizumab treatment while waiting for confirmation of PD if they are clinically stable as defined by the following criteria:

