## 8.11 Primary Objectives

Objective response rate as defined by achieving complete response and/or partial response will be presented by percentage rates and 90% CIs. All response assessments will be listed.

Note that the Disease Assessment time point used for this analysis may vary, and need not be the first on treatment assessment. Where there is the possibility of an immune response leading to a false categorization of disease progression, results from later tumor imaging time points may be used for the ORR assessment following the  $k$ -stage design.

Objective response rate is defined as the percentage of patients with a CR or PR (out of the number evaluable), a 90% CI for the overall ORR will be calculated assuming an exact binomial distribution.

A patient who has discontinued both treatments, and subsequently responds having received a subsequent anti-cancer treatment may be excluded (at the statistical analysis) from the subset of responding patients (these patients are evaluable, and will be included in the denominator). Such patients will contribute to the time to progression and death Kaplan Meier plots.

All patients with a documented PR or CR are expected to have the result confirmed by repeat scan at least 4 weeks (28 days) later.

The ORR will further be explored as follows:

- By PD-L1 status (+ve/-ve), using a Chi square or Fishers Exact Test
- By Axl status (+ve/-ve), using a Chi square or Fishers Exact Test, and
- Summarized in a table of PD-L1 by Axl expression status to explore the ORR in each of the four quadrants (++, +-, -+, --). That is, patients will be allocated into one of the 4 groupings: where both Axl and PD-L1 are positive; where there is one positive and one negative and where there are both Axl and PD-L1 negative.

If the PD-L1 expression status is provided as a TPS or, in one of 3 categories usually <1%, 1-49% and  $\geq 50\%$ , the patient will be regarded as PD-L1 positive if their TPS is  $\geq 1\%$ .

A patient with Axl positive disease is defined as one with an expression level of 1+ or greater according to IHC staining intensity, although other cut offs may be considered.

For each patient, the best percentage change in tumor volume will be illustrated in a ‘waterfall’ plot.

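### A new lesion that persists but is stable on repeat imaging is PD by Table 21 but not confirmed PD by Section 8.5.1, and Sections 8.11 and 4.1 leave it optional whether later scans count for ORR

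*Protocol*

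**What the plan says.** Protocol Section 5.3.10 names the criterion: "Efficacy endpoints in this study, including ORR, DoR, PFS will all be based on tumor imaging evaluation by RECIST 1.1". Section 8.5 repeats this.

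The rules for a new lesion are spread over several places:

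- **Section 8.5, text after Table 20.** A new lesion is assessed as progression, although treatment can go on if the patient is not deteriorating. For a lesion that is equivocal at first: "If repeat scans confirm there is a new lesion, then the progression date should be declared using the date of the initial scan". The same section says that progression must be confirmed, but not what confirms it when a new lesion is simply still there.
- **Table 21.** Any target-lesion status and any non-target status, combined with a new lesion, gives an overall visit response of PD. There is no row for a new lesion that is stable.
- **Section 8.5.1.** RECIST 1.1 is used with adaptations because the standard form may misjudge response to immunotherapy. One condition for continuing treatment after the repeat scan is "stable or improved previous new lesion (if identified as cause for initial PD"). The scenarios that confirm PD include "New lesion resulting in initial PD is worse (qualitative") and the appearance of an additional new lesion. A stable new lesion is not among them.
- **Section 8.11.** Where a false categorization of progression is possible, "results from later tumor imaging time points may be used for the ORR assessment following the" k-stage design. Section 4.1 has a parallel sentence. Neither says who decides, when, or whether all such patients are handled alike.
- **Section 8.12.2.3.** PFS runs to the first observation of progression. It is not stated whether a progression that is never confirmed is an event.

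**The concern.** Response is the primary endpoint and the decision rule works on small integer counts, so each patient's classification has to be fixed in advance. Here a patient with a persisting, unchanged new lesion can be classified in two ways, each with support in the text. Section 8.11 then makes the choice optional for the primary endpoint.

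The option applies only to patients already categorized as progressing. Compared with Table 21 it can therefore move patients into the response count but never out of it. The trial is open-label, scans are read by the local investigator (Sections 5.3.10 and 8.5), and the committee that documents the ORR at the end of Stage 1 includes Principal Investigators and sponsor medical monitors (Sections 8.2.1 and 8.2.2). A one-directional, unassigned choice in that setting permits bias. The same gap reaches DCR (SD or PD) and PFS (event or no event).

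**Working it through.** **1. One set of scans under both rules.** Take a hypothetical patient on the Table 3 schedule. An unequivocal new lesion appears at Week 10 and is unchanged at Weeks 19 and 28. Target lesions are 35% below baseline at Weeks 19 and 28, and non-target disease is not progressing.

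| Step | Table 21 | Section 8.5.1 with the Section 8.11 option |
|---|---|---|
| Week 10 | PD (new lesion) | Initial PD, to be confirmed |
| Week 19 | PD (new lesion present) | Not confirmed: lesion not worse, no further lesion |
| Week 28 | PD | Target-lesion PR seen again 9 weeks later, beyond the 4-week minimum |
| ORR | Non-responder | Responder, if later scans are used |
| PFS | Event at Week 10, if visit PD counts | No event by Week 28, if only confirmed PD counts |

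If the target lesions had only been stable, ORR would not change, but DCR and PFS would still differ.

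Had the Week 10 lesion been equivocal, the quoted Section 8.5 sentence would declare progression at Week 10 once a repeat scan showed that the lesion exists. Taken together, a doubtful lesion that persists unchanged is back-dated progression, while a definite one that persists unchanged is not confirmed progression under Section 8.5.1.

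**2. The design as stated.** Inputs from Section 8.1: p0 = 0.20, p1 = 0.35, 28 patients per stage. The futility rule is: "If 5 or fewer responses are observed in these 28 patients, the trial will be terminated in favor of the null for futility". Eleven responses or more at that look stop the trial for activity. The final rule is: "If a total of 17 or more responses are seen in 56 patients, then the null will have been rejected". With X1 and X2 independent Binomial(28, p):

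P(declare activity) = P(X1 ≥ 11) + Σ (x = 6 to 10) P(X1 = x) × P(X2 ≥ 17 − x)

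- p = 0.20: P(X1 ≤ 5) = 0.5005, P(X1 ≥ 11) = 0.0149, total 0.0483 (stated: futility stop 50.2%, Type I error 0.048).
- p = 0.35: P(X1 ≥ 11) = 0.384, total 0.8055 (stated 38.4% and 80.6%).
- Expected size: 28 + 28 × (1 − 0.5005 − 0.0149) = 41.6 under the null and 28 + 28 × (1 − 0.0393 − 0.384) = 44.1 under the alternative (stated 42-44).

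The design figures reproduce.

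**3. What one patient can change.** One reclassification turns 5 into 6 of 28 (futility stop becomes continuation), 10 into 11 of 28 (continuation becomes stop for activity), or 16 into 17 of 56 (null not rejected becomes rejected). Probabilities of landing exactly one below a cut-off:

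- p = 0.20: 0.1856 + 0.0242 + 0.0313 = 0.241
- p = 0.35: 0.0257 + 0.1553 + 0.0598 = 0.241

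The terms overlap slightly, because a trial with 10 of 28 can also end with 16 of 56.

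**4. Sensitivity only.** The protocol gives no rate of response after an initial PD, so a shift of 1 to 3 percentage points is an assumption. Using the formula in step 2:

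| Shift | Null rate after lenient counting | P(declare activity) | Alternative rate after strict counting | Power |
|---|---|---|---|---|
| 0 | 0.20 | 0.048 | 0.35 | 0.806 |
| 1 point | 0.21 | 0.070 | 0.34 | 0.761 |
| 2 points | 0.22 | 0.099 | 0.33 | 0.710 |
| 3 points | 0.23 | 0.134 | 0.32 | 0.654 |

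**The case against.** Several points on the other side have force.

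- The quoted sentence concerns equivocal lesions. It asks whether the finding is a new lesion at all, and Section 8.5.1 then asks whether an initial PD is confirmed, so the two could run in sequence. This stands as a limit: for an unequivocal lesion the conflict is between Table 21 and Section 8.5.1. It does not remove the conflict, because the equivocal-lesion sentence declares progression on existence alone.
- Table 21 is a visit-level algorithm, and Section 8.5 itself requires confirmation. That is correct, so it would be wrong to say that Section 8.5 has no confirmation step. But it does not say what confirms progression when a new lesion merely persists.
- The bullets in Section 8.5.1 mainly steer treatment, so one could let them govern treatment and Table 21 govern endpoints. The protocol does not say this. Section 8.5.1 gives response assessment as its reason, and Section 8.11 carries the idea into ORR.
- Section 8.3 leaves data handling to the SAP, which is not shown. A SAP could settle the derivation. It could not recover scans never taken: imaging runs until confirmed progression, and a site that treats persistence as confirmation may stop imaging.

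A reader might also infer more than the text supports. Nothing says that the Section 8.11 choice will be made patient by patient or after the count is known, and responses are still expected to be confirmed at least 28 days later. Sections 5.3.10 and 8.5 do not say that the first unequivocal PD ends response assessment, so strict RECIST cannot be presented as the rule already chosen.

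**Conclusion.** The inconsistency is real and should be corrected. The protocol classifies a persisting, stable new lesion in two ways, does not say whether unconfirmed PD is a PFS event, and makes the use of later scans for the primary endpoint optional. ORR is affected only if the target lesions also reach a confirmed response and the option is used; otherwise DCR and PFS are affected.

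For ORR the direction is known: the option can only add responders. The size is not known. The range of 7.0% to 13.4% against 4.8% shows how steeply this design reacts to 1 to 3 added points under the null. It is an operating characteristic at assumed rates of 21% to 23%, and patients with a stable new lesion and a confirmed response are only some of those whom Section 8.11 could reach. It should not be read as the trial's actual Type I error. No stated design figure is wrong.

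**What to change.** Before the interim analysis:

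1. Name one criterion as primary for ORR, DoR, DCR and PFS, either RECIST 1.1 by Table 21 or the confirmed-PD rule of Section 8.5.1. Apply it to every patient by algorithm, and report the other for every patient as supportive. Either choice removes the ambiguity. Table 21 fits the criterion named in Section 5.3.10, while the confirmed-PD rule fits the rationale in Section 8.5.1.
2. Replace the optional wording in Sections 8.11 and 4.1 with that fixed rule.
3. Make Section 8.5, Table 21, Section 8.5.1 and Section 8.12.2.3 agree on a new lesion that persists but is stable, and on whether unconfirmed PD is an event.
4. Reconcile the treatment-continuation wording separately. No view is taken here on what that rule should be.

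The cost is protocol and SAP wording and one extra derived response variable from scans already collected. If the stricter rule is made primary, the primary ORR may be slightly lower, and the power column above shows the price under the same assumed shifts.
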